## G2. Data Analysis

Provide a description of your plan for data analysis. State the types of comparisons you plan (e.g. comparison of means, comparison of proportions, regressions, analysis of variance). Which is the PRIMARY comparison/analysis? How will the analyses proposed relate to the primary purposes of your study?

Study 1: The analysis of the qualitative data will include reviewing the parent and child responses from the audiotaped interviews and focus groups and notes taken by staff during these sessions. The content will be transcribed and coded for themes.

Study 2- Distributional characteristics will be assessed and outliers checked for accuracy. Prior to inferential procedures, standard descriptive statistics will be calculated for demographics. Psychometric analysis of food and physical activity parenting practices: The fit of each item to the proposed subscales of the Food and PA parenting practice scales (proposed latent variable) will be evaluated using confirmatory factor analysis (CFA) and item response modeling (IRM). The fit of competing models will be tested (i.e., one-factor versus two-factor versus three-factor, etc.) using a combination of absolute and relative fit indices such as the chi-square statistic and ratio of chi-square to degrees of freedom, the root mean square error of approximation (RMSEA), incremental fit index (IFI) and comparative fit index (CFI) as recommended by Hoyle and Panter. Standardized residuals and modification indices will also be examined. Because the chi-square is sensitive on the sample size, assessing both absolute (i.e., RMSEA) and incremental (i.e., normed fit index, NFI and CFI 82) fit indices is recommended. The criteria of an acceptable model fit include: RMSEA less than, or equal to 0.08, and NFI and CFI greater than 0.90, while a good model fit is obtained when RMSEA less than, or equal to 0.05, and NFI and CFI greater than 0.95. Hu and Bentler's two-index presentation strategy will be used as an alternative criteria, if necessary. These and item content will be used to determine whether an item should be retained or removed from the model. Cronbach coefficient alpha reliabilities will be computed for each subscale of the final model, to assess the internal reliability. IRM analysis will be performed to (1) evaluate the response categories, (2) estimate the item and person difficulty parameters, (3) test item fit using infit and outfit criteria, (4) estimate the reliability across the full range of the scale, (5) produce a Wright map linking individual and item distributions, and (6) conduct Differential item functioning by fathers race/ethnicity and educational status. Intra-class correlation coefficients (ICCs) will be computed to establish the test-retest reliability of the Food and PA parenting practice subscales from the sub-sample, using absolute agreement in two-way random models. ICC values up to .20 denote poor reliability; .21-.40 fair reliability; .41-.60 moderate reliability; .61-.80 substantial level of reliability; and > .80 excellent reliability. Regression models will assess demographics, coparenting alliance, and division of labor in household as predictors of physical activity and food parenting practices. Cluster analysis will explore profiles of father's use of parenting practices.

Study 3- Exploratory Analysis: Distributional characteristics will be assessed and outliers checked for accuracy. Prior to inferential procedures, standard descriptive statistics will be calculated for demographics, anthropometric and behavioral data, and data assessed for non-normality and transformation applied where appropriate. Analysis of Covariance (ANCOVA) will assess the group difference of father's weight after controlling for father's weight at baseline and potential covariates (father's education, household income and child gender), and group membership will be treated as the between subjects factor. Prior to conducting the ANCOVA, the homogeneity of regression assumption will be tested. This approach will also be used to assess the effect on children's BMI z-scores, and the father's and children's behaviors. Correlations of the father's and child's carotenoid intake as measured by the food frequency questionnaire will be compared to the average of the dermal carotenoid assessments at baseline as well as the correlation of the change of the reported and dermal assessments from T0-T1.

Feasibility Criteria for Study 3: Retention of subjects in study assessments 1. Retain 80% of intervention and control participants for pre- and post-assessments 2. Recruit 40 Latino fathers and their families in ≤ 4 months 3. Maintain ≥70% attendance to program sessions 4. The participating Latino fathers will be satisfied with the program as measured by 80% excellent-good satisfaction from questionnaires and exit interviews with the Latino fathers and their co-parent (typically children's mother). 5. Ability to collect anthropometric, behavioral and parenting data on at least 75% of the Latino fathers and anthropometric, and behavioral data on their children (both groups) at baseline and follow up

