## Section G: Sample Size/Data Analysis

### G1. Sample Size

How many subjects (or specimens, or charts) will be used in this study?

Local: 1540      Worldwide: 1540

Please indicate why you chose the sample size proposed:

Study 1: We will recruit Latino fathers (n=25) and mothers (n=10) to serve on a Panel of Latino Parents as key informants to help advise on the cultural adaptation of HDHK. It is possible that some parents may drop out during the course of the study. If that occurs they will be replaced. We anticipate this may happen to up to 50% of the sample. We will recruit up to 30 children to participate in the child focus groups. TOTAL SAMPLE FOR STUDY 1 n=100.

Study 2: We will recruit 1200 fathers for the cross-sectional study in order to have 600 who qualify and complete the full survey. There are no exact sample size requirements for planned estimation procedures such as Confirmatory Factor Analysis (CFA), or Item Response Modeling (IRM), due to the complexity of issues involved in the determination of a sample that provides stable estimates. However, general guidelines based on the ratio of subjects to variables exist (e.g., at least 5-10:1). Others recommend at least 100 to 150 participants are needed to avoid non-convergence or improper solutions of models by CFA, or a simulation study reporting a wide range of sample size (from 30 up to 450) with rather small lower bound sample size as enough. For adequate samples for IRM analysis, samples of 100 were proposed when there are few model parameters and samples of 200-500 for IRM models with larger number of parameters. To conduct differential item function (DIF) analysis within IRM, by race/ethnic groups, samples of 100-200 per group will be required. Therefore, a sample of 600 fathers should afford adequate power for evaluation of a 25-40 item instrument via CFA, IRM and DIF analyses. TOTAL SAMPLE FOR STUDY 2, n=1200.

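### Study 2 makes NFI above 0.90 a condition of acceptable fit; in a pooled 25-40 item CFA with 600 fathers and moderate loadings, a correct model can miss it

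*Combined protocol and SAP*

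**What the plan says.** Section G2 (Data Analysis, Study 2) compares competing factor models, described as "one-factor versus two-factor versus three-factor, etc", for the food and physical activity parenting scales. The indices it first announces include "incremental fit index (IFI) and comparative fit index (CFI". It then remarks that chi-square is sensitive to sample size and recommends absolute and incremental indices together, giving NFI and CFI as the incremental ones.

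The rule for acceptable fit is "The criteria of an acceptable model fit include: RMSEA less than, or equal to 0.08, and NFI and CFI greater than 0.90". The higher label follows: "while a good model fit is obtained when RMSEA less than, or equal to 0.05, and NFI and CFI greater than 0.95". IFI receives no cut-off. A fallback is allowed: a "two-index presentation strategy will be used as an alternative criteria, if necessary", without a stated trigger or cut-offs. On the use of the results, after mentioning residuals and modification indices as well, the plan says: "These and item content will be used to determine whether an item should be retained or removed from the model".

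Section G1 (Sample Size, Study 2) supplies the dimensions: "a sample of 600 fathers should afford adequate power for evaluation of a 25-40 item instrument via CFA, IRM and DIF analyses".

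**The concern.** The three conditions for acceptable fit are joined by 'and', so NFI alone can deny the label. NFI compares the model chi-square with the baseline chi-square and makes no allowance for degrees of freedom. With many items, a correct model still has a chi-square of about its degrees of freedom, which can be several hundred. NFI therefore stays visibly below 1 however well the model fits, and how far below depends on sample size. That is the weakness for which the plan sets chi-square aside.

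At stake is Specific Aim 2, the validation of these scales as possible mediators for the later trial. A rule that can mark a correct model unacceptable, and that improves when items are dropped, leans towards shorter scales for reasons unrelated to misfit.

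**Working it through.** **The plan's own figures.** G1 gives no power formula and no expected NFI, so there is no power figure to reproduce. Its rule of thumb is "general guidelines based on the ratio of subjects to variables exist (e.g., at least 5-10:1"; 600/25 = 24 and 600/40 = 15 fathers per item, so that rule is met. The sample size is not the issue.

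**Inputs.** From G1: N = 600 and p = 25 to 40 items. Assumed, because the documents give none: number of factors k, common loading λ, factor correlation φ, maximum-likelihood estimation, and one CFA on the pooled items.

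**Formulas.** NFI = 1 − χ²(model)/χ²(baseline). Under a correct model χ²(model) averages its degrees of freedom, so NFI ≈ 1 − df/χ²(baseline), where

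- df = p(p+1)/2 − 2p − k(k−1)/2;
- χ²(baseline) ≈ p(p−1)/2 + (N−1)F, with F = −ln|R| and R the item correlation matrix that the model implies.

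With m = p/k items per factor, R has eigenvalues 1−λ² (p−k times), 1+(m−1)λ²−mφλ² (k−1 times) and 1+(m−1)λ²+(k−1)mφλ² (once).

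**Worked case: 40 items, 5 factors, λ = 0.6, φ = 0.4.** df = 820 − 80 − 10 = 730. The eigenvalues are 0.64 (35 times), 2.368 (4 times) and 8.128 (once), so F = 10.08. χ²(baseline) ≈ 780 + 599 × 10.077 = 6816, and NFI ≈ 1 − 730/6816 = 0.893. The simulated mean was 0.891.

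**Dependence on sample size, same correct model.** N = 300: 1 − 730/3793 = 0.81. N = 600: 0.89. N = 1200: 1 − 730/12862 = 0.94.

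**Simulation of exactly correct models, N = 600.** The grid used 25, 30, 35 and 40 items; 1, 3, 5 and 7 factors; and φ of 0.3 or 0.5. It had 28 cells per loading and 200 replicates per cell.

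| Loading | Mean NFI across cells | Average P(NFI > 0.90) | Average P(NFI > 0.95) |
|---|---|---|---|
| 0.4 | 0.66-0.85 | 0 | 0 |
| 0.5 | 0.80-0.92 | 0.07 | 0 |
| 0.6 | 0.88-0.95 | 0.73 (0 to 1.00 by cell) | 0.01 |
| 0.7 | 0.925-0.967 | 1.00 | 0.35 (0 to 1.00 by cell) |
| 0.8 | 0.954-0.979 | 1.00 | about 1.00 (0.92-1.00 by cell) |

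At 0.5, 26 of 28 cells passed 0.90 less than half the time. At 0.6 this was so in 8 of 28. Seven of those had 35 or 40 items with 5 or 7 factors, and the eighth had 30 items with 7 factors.

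**Mixed loadings.** Full maximum-likelihood fits used 5 factors, φ = 0.3 and 60 replicates per cell. With loadings from 0.4 to 0.8, P(NFI > 0.90) was 1.00 at 25 items and 0.45 at 40 for continuous items, and 0.85 and 0.00 for five-category items treated as continuous. With loadings from 0.5 to 0.8 it was 1.00 for continuous items and 0.77 to 1.00 for five-category items. P(NFI > 0.95) was at most 0.02 throughout.

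**The other indices.** In 21 equal-loading maximum-likelihood cells every replicate had CFI above 0.95, and the largest RMSEA was 0.043. In the mixed-loading cells mean CFI was 0.994-0.997, mean IFI 0.996-1.000 and mean RMSEA 0.005-0.008. The NFI failures are therefore not signs of misfit.

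**Effect of shortening.** With 5 factors, λ = 0.6 and φ = 0.3, a correct model has mean NFI 0.890 at 40 items (1 − 730/6632) and 0.918 at 25 (1 − 265/3195 gives 0.917). One-factor models of 5-8 items reached mean NFI of 0.965-0.992.

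**The case against.** The strongest reply is that the result rests on quantities the plan does not state. With loadings of 0.7 or more every simulated correct model passed 0.90. G2 speaks of the fit of items to proposed subscales and does not say whether one pooled CFA or separate ones will be run; short one-factor subscales are largely unaffected. This stands, and it makes the point conditional. It does not remove it: G1 justifies the sample by CFA of a 25-40 item instrument, and comparing one, two and three factors means pooling items across factors.

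Nor does NFI act alone. The plan also uses RMSEA, CFI, residuals, modification indices, item content and item-fit statistics from the item response model. NFI describes a whole model and singles out no item for deletion. The two-index fallback could rescue a correct model that fails on NFI. All of this reduces the risk. What remains is that the stated rule requires NFI, and that the fallback has no trigger.

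A reader might infer more: that a correct model cannot pass, that missing 0.95 fails a scale, or that good items will be deleted. The documents support none of these. The first is contradicted by the results at 0.7 and 0.8. The 0.95 level only confers the label 'good'. Nothing in G2 says that items are dropped until NFI passes. Harm to Study 3 is likewise undocumented: its procedures list a parenting practices survey without saying that it is the version trimmed in Study 2, and none of its feasibility criteria depends on CFA fit.

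**Conclusion.** The point holds conditionally. If the CFA is fitted to the pooled 25-40 items with 600 fathers, requiring NFI above 0.90 can label an exactly correct model unacceptable. This is usual at loadings of 0.5 or lower. At about 0.6 it occurs mainly towards 35-40 items or with many factors. Reaching 0.95 is rare at 0.6 and happens in about a third of replicates at 0.7, but this affects only the upper label. The rule could misjudge a sound scale and favours shorter ones; it is not shown that it would. The lack of a degrees-of-freedom correction and the dependence on sample size need no assumption about loadings. The pass rates do, and they also rest on simple structure and the assumed factor counts and correlations.

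**What to change.** In both fit-criteria sentences of G2, replace NFI by IFI, which the plan already names, and keep the cut-offs: acceptable if RMSEA ≤ 0.08 with IFI and CFI > 0.90; good if RMSEA ≤ 0.05 with IFI and CFI > 0.95. Judging on CFI and RMSEA alone would serve equally well. Report NFI descriptively only. The two-index alternative may stay; stating when it applies would help but is not needed for this point.

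The cost is a small wording change. IFI is routine output, and neither the data collection nor the sample size changes.

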### Section F: Design/Procedure

#### F1. Design

Select one category that most adequately describes your research:

c) Pilot

Discuss the research design including but not limited to such issues as: probability of group assignment, potential for subject to be randomized to placebo group, use of control subjects, etc.

Study One (SA 1) consists of qualitative studies (focus groups and interviews) with Latino parents to assist with culturally adapting the HDHK curriculum for a US Latino population.

Study Two (SA 2) is a cross-sectional study of a multi-ethnic/racial sample of fathers to complete a secure internet survey on physical activity and food parenting practices. Two weeks later, a sub-set of fathers will be asked to complete the surveys again.

Study Three (SA 3 and Exploratory Aim) is a feasibility study where Latino fathers and their families enroll and will be randomized to participate in the HDHK program immediately (Intervention group) or wait-listed several months to participate (Control group).

Inclusion Criteria:

Study 1: 1) Latino fathers and mothers with at least one healthy child between the ages 5-11 years old whose child is seen at the TCHP Center Clinic, 2) able to read and write in either Spanish or English. 3) Latino families who live in the Greater Houston area.

Study 1 Child Focus Group: 1) healthy Latino child between the ages 5-11 years old seen at the TCHP Center Clinic, 2) able to read and write in either Spanish or English.

Study 2: 1) Father of child between the ages of 5-11 years, whose child is able to participate in regular physical activities and eat regular foods, 2) able to read and write in either Spanish or English (although audio assistance of survey will be available for those that have lower literacy levels).

Study 3: 1) Latino fathers, mothers (if available) over the age of 18, with at least one healthy child between the ages 5-11 years old, and target child between the ages of 5-11 years old, 2) Child is a patient at one of the TCHP Center for Children and Women Clinics, 3) parents able to read and write in either Spanish or English. 3) Latino families who live in the Greater Houston area. 4) Latino fathers and children willing to wear an accelerometer for a 7 day study period at baseline and 4 months later. 4) Latino fathers with a BMI > 25, 5) Fathers pass the American College of Sports Medicine (ACSM) health screener to participate.

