The specific questions asked during the subsequent focus groups and interviews will depend on the first round of adaptations by the BCM research team, and guide/scripts will be added to IRB protocol when available and prior to focus groups or interviews starting. Parents will be consented at the first visit and re-consent will only be obtained later in the study if subsequent changes results in amendments that affect participation in protocol or affect subjects in other ways. The first focus group session will consist of reviewing the HDHK program goals, curriculum outline and content of sessions of the HDHK program, in English or Spanish. Future discussions will be held regarding the Ecological Validity Model dimension (including: (1) language, (2) persons, (3) metaphors, (4) content, (5) concepts, (6) goals, (7) methods, and (8) context) and how these apply to HDHK, including components they feel do not engage them or do not apply to them. They will be asked to offer alternative content or methods of delivering the same content that is more applicable to them. They will also be asked to make suggestions of new content areas they feel should be covered by the program to help them engage with their families in being more active and eating healthier. Issues regarding co-parenting, communication between the father and his partner (often child's mother), and cultural values such as simpatia, collectivism, respeto, and familism will specifically be explored.

Contact two will be either 1) cognitive interviews to assess their understanding of each of the Food and PA items selected for study 2; or 2) an on-line survey with follow up interview. If parent desires, they can participate in both, if within the limit of five contacts during the study.

Cognitive interviews: Up to 20 Latino fathers from the parent panel will be interviewed, in iterative rounds of cognitive interviews to assess resulting changes in survey questionnaire from previous cognitive interview findings. They will also be asked to comment on the possible response options, and instructions of the survey instrument. The full survey questionnaire and cognitive interview script is attached in section S. The survey questionnaire and cognitive interview will be provided in English or Spanish depending on the participants' preference.

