Study Two: A cross-sectional multi-ethnic/racial sample of fathers (n=600) will be recruited to complete an on-line study that includes a demographic survey, physical activity parenting practice survey, food parenting practice survey, the Co-parenting Alliance survey, and the Pew Research division of labor in the household survey. Fathers will complete surveys administered via a secure internet survey. The secure internet survey will have a cover letter of consent followed by survey questions. Fathers will be instructed to answer the items regarding what they do themselves to parent their child. If fathers do not have access to a computer or internet service at home, computers will be made available at the CNRC, TCHP Center clinics or community centers for them to use. Contact information will be requested to process payment and to recontact a sub-sample of the Father in 2 weeks. Participants can opt out of providing contact information but will then not receive payment. The survey will have audio-links to listen to the cover letter or individual survey questions for those fathers with limited literacy levels. Ninety of the fathers will be asked to complete the surveys again 2 weeks later to assess the test-retest reliability of the instruments in 15% of the sample. The full survey and cover letter are attached in Section S.

Study Three: The procedures for Study 3 are Attached in Section S due to space limitations. Clinical Trials Registration: NCT03532048

Add-on Study to Study 3 (Feasibility of assessing arterial stiffness in future trials of Papas Saludables, Ninos Saludables): procedures are attached in Section S due to space limitations

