**Mode of Advertising: Internet**

Exact language of Advertisement:

Study 2 Encuesta por internet para PADRES - acerca de cómo interactúan con su niño para promover la actividad física y alimentación.

CNRC, Hospitales del Centro Médico, negocios ¿ Páginas de voluntarios ¿boletín informativo:

Se invita a Padres con niños de 5-11 años para contestar una encuesta por internet de 30 minutos acerca de lo que él hace con su niño(a) para promover la actividad física y la alimentación. Recibirá \$15 por contestar la encuesta. Si está interesado, llame a [name] al [contact] o por correo electrónico a [[contact]](mailto:[contact]) acerca del Estudio de PADRES. O abra el link: [www.healthydads.net](http://www.healthydads.net)

Long Versión: Investigadores del Centro de Investigación de Nutrición Infantil del Colegio de Medicina de Baylor están buscando a Padres con niños de 5-11 años para contestar una encuesta por internet de 30 minutos acerca de sus interacciones con su niño(a) para promover la actividad física y la alimentación. Recibirá \$15 por contestar la encuesta. Si está interesado, llame a [name] al [contact] o por correo electrónico a [[contact]](mailto:[contact]) acerca del Estudio de PADRES. O abra el link: [www.healthydads.net](http://www.healthydads.net)

Short Versión: Se invitan Padres con niños de 5-11 años para contestar una encuesta por internet de 30 minutos de lo que él hace con su niño(a) para promover la actividad física y la alimentación. Centro de Investigación de Nutrición Infantil del Colegio de Medicina de Baylor. Recibirá \$15 por contestar la encuesta. Si está interesado, llame a [name] al [contact] o por correo electrónico a [[contact]](mailto:[contact]) acerca del Estudio de PADRES. O vaya a la página: [www.healthydads.net](http://www.healthydads.net)

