#### For Dads and Moms:

2. Demographics
3. Food and physical activity parenting practices survey
4. Co-parenting alliance survey
5. Acculturation (Bi-Acculturation Scale) survey
6. Respeto (Respect sub-scale from the Mexican-American Cultural Values scale) survey
7. Pan-American familism survey.
8. Program Satisfaction Survey at the end of the program

Data will be collected at the TCHP Center Clinic where the program will be delivered. All data collection tools, survey packets for Father, child and mother, and the accelerometer wear log for fathers and children are attached in Section S. Data will be collected and managed by RedCap (via the BCM institutional contract). If data needs to be collected on hardcopies, they will be manually entered by staff and verified by a second staff. Hardcopies will be stored in the participant's study file in the locked study cabinet, in the study manager's office that is a federal building with 24 hour security (CNRC). The food frequency questionnaire (FFQ) is not attached because is an online purchase assessment tool which can be find at: Block Dietary Data Systems: [www.nutritionquest.com](http://www.nutritionquest.com). Nutrition Quest will help process the nutrition data that is coded with the participant's study ID. Nutrition Quest will not have access to any HIPPA related

data, nor identifying information on the participants. The only modification to the FFQ is if the child or father state they consume “other fruit” or “other vegetables” more than 3 times a week, which other fruit and vegetables they consume will be probed to get a more accurate carotenoid intake value. If the father or child states they

After baseline data are collected, families will be stratified into preferred language of program (English or Spanish) and randomly assigned to receive the program immediately (Intervention Group) or after a 5-7 month waitlist period (Control group). The culturally adapted HDHK program, called Papás Saludables, Niños Saludables, is a 10 week program for fathers and their children that meets weekly. Each participating father and child will be given a Papás Saludables, Niños Saludables T-Shirt to wear to program sessions to promote group cohesion (collectivism).

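### Study 2 checks item bias by race/ethnicity and education but not by survey language, so a faulty Spanish item is diluted in the Latino contrast or cannot be told from an ethnic difference

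*Combined protocol and SAP*

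**What the plan says.** G2 (Data Analysis, Study 2) lists six uses of item response modeling. The last is to "conduct Differential item functioning by fathers race/ethnicity and educational status". No other grouping is named. The factor analysis, item fit, alpha and test-retest ICC are described without a split by language. G2 gives no rule for what happens to an item that shows DIF; items are kept or removed on fit, residuals, modification indices and content.

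Several sections show that Spanish responders are intended:

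- F1 (Design) admits fathers "able to read and write in either Spanish or English (although audio assistance of survey will be available" for those with lower literacy.
- Section R (Mode of Advertising: Internet) carries a Spanish notice for this survey: "Se invita a Padres con niños de 5-11 años para contestar una encuesta por internet de 30 minutos".
- F2 (Procedure, Study One), on cognitive testing of the items chosen for Study 2, states: "The survey questionnaire and cognitive interview will be provided in English or Spanish".

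On size, F2 states: "A cross-sectional multi-ethnic/racial sample of fathers (n=600) will be recruited". No quota by language or ethnicity is set. For DIF by race/ethnic group, G1 (Sample Size) says that "samples of 100-200 per group will be required", and concludes that "a sample of 600 fathers should afford adequate power for evaluation of a 25-40 item instrument via CFA, IRM and DIF analyses".

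The Study 3 supplemental file gives the parenting survey to fathers and mothers. Before randomization, "families will be stratified into preferred language of program (English or Spanish").

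**The concern.** SA 2 is meant to deliver food and physical activity parenting scales that are valid for Latino fathers. If an item reads differently in Spanish, two fathers with the same practices score differently on it because of the language version. Neither planned grouping isolates this. Latino fathers may answer in either language, so the race/ethnicity contrast averages a Spanish fault with English responses that do not carry it. Education is at best a loose proxy for language.

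Two things can then go wrong. The fault can be too diluted to be noticed, or it can be noticed and read as an ethnic difference in parenting. Either way it enters the final scales. It also enters the Study 2 regressions on demographics and the cluster profiles, where any predictor related to language would pick up part of the translation shift.

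**Working it through.** **1. The plan's own figure.** At 5-10 fathers per item, 25-40 items need 25 x 5 = 125 to 40 x 10 = 400 fathers. For DIF, 600 = 3 groups x 200 or 6 groups x 100. So 600 is consistent with the G1 guide. It cannot be derived uniquely, because the number of groups, the DIF size, alpha and power are not given. Language groups do not enter it.

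**2. Dilution.** Let s be the Spanish share of Latino fathers and d the shift in the Spanish item. Assume that other fathers answer in English and that there is no true ethnic difference on the item. Then

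apparent Latino contrast = s x d.

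For the contrast to reach 0.5 logit, d must be 0.5/s: 2.0 at s = 0.25, 1.0 at 0.50, 0.67 at 0.75 and 0.5 at 1.

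**3. Normal approximation.** Assumptions: 200 Latino and 400 other fathers, d = 0.4 SD, two-sided alpha 0.05.

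- Race/ethnicity: SE = sqrt(1/200 + 1/400) = 0.087. Apparent shifts of 0.10, 0.20 and 0.30 SD give power 0.21, 0.64 and 0.93 at s = 0.25, 0.50 and 0.75.
- Language within Latino fathers: SE = sqrt(1/50 + 1/150) = 0.163 for a 50/150 split and sqrt(1/100 + 1/100) = 0.141 for 100/100. Power is 0.69, 0.81 and 0.69.
- With only 100 Latino fathers (500 others), the race/ethnicity contrast misses the fault with probability 0.85 at s = 0.25 and 0.55 at s = 0.50.

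**4. Simulation.** Ordinal item, matched on the rest score, 200 Latino and 400 other fathers, 1000 runs per setting (Monte Carlo error up to about 3 points). Share of runs in which the fault is detected:

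| Shift (logit) | Test | s = 0.25 | s = 0.50 | s = 0.75 |
|---|---|---|---|---|
| 0.6 | Race/ethnicity | 0.13 | 0.42 | 0.72 |
| 0.6 | Language within Latino | 0.42 | 0.58 | 0.45 |
| 0.8 | Race/ethnicity | 0.21 | 0.61 | 0.93 |
| 0.8 | Language within Latino | 0.68 | 0.82 | 0.68 |
| 1.0 | Race/ethnicity | 0.31 | 0.82 | 0.99 |
| 1.0 | Language within Latino | 0.85 | 0.93 | 0.85 |

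With no shift, both tests reject in about 5-6% of runs. The ranking reverses at s = 0.75.

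**5. Education as a proxy.** Assume that 25-30% of lower-education and 3-8% of higher-education fathers answer in Spanish (300 v 300), and d = 0.5 SD. The contrast is (0.25 - 0.08) x 0.5 = 0.085 SD to (0.30 - 0.03) x 0.5 = 0.135 SD, with power 0.18 to 0.38.

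**6. Limits of the added contrast.** A smaller simulation (120 runs, five-category item, 100 v 100, true shift 0.8 logit) gave a mean estimate of 0.78 and 82% significant. This implies SE = 0.78/(1.96 + 0.92) = about 0.27. Then:

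- For a 0.4-logit shift, 0.4/0.27 = 1.48, so power is about 30%.
- With no shift, an estimate beyond 0.5 in either direction has probability of about 6% (0.5/0.27 = 1.85). Over 25-40 items that is about two false flags.
- Two language groups of 100 need 200 Latino fathers if evenly split, and 100/0.25 = 400 at a 25/75 split. With 150 Latino fathers an even split gives 75 v 75.

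**The case against.** The strongest defense has four parts.

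**Translation is already checked.** Up to 20 Latino fathers are interviewed, in English or Spanish, on their understanding of each item, with revisions between rounds. This lowers the chance of a gross fault. It is qualitative, however, and does not test whether the two versions behave alike. Pooled item fit averages over versions, and a retest ICC does not see a stable shift if a father answers in the same language twice.

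**The planned test may do well.** A reader might infer that it is blind to Spanish faults. That goes too far: at a 75% Spanish share it detects a 0.8-logit shift more often than the language contrast does. What remains there is attribution.

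**Study 3 is less exposed than it looks.** A reader might infer that pooling over languages will bias the Study 3 results or the later mediation work. The documents do not support this. The G2 analysis for Study 3 names weight, BMI z-scores and behaviors, not the parenting scales, so pooling them is an inference. A constant shift largely cancels in within-father change if the survey language stays the same. Stratification by program language should roughly balance it between arms if survey language follows program language. The one Study 3 feasibility criterion that touches these data concerns their collection, not their level.

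**No harmful action is written into the plan.** A reader might also infer that a flagged item would simply be dropped. G2 has no such rule, and its use of item content leaves room to recognize a wording fault.

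The last three points narrow the consequence. None supplies a check of language equivalence.

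**Conclusion.** The concern holds in a limited form. G2 omits the one DIF grouping that would test equivalence of the Spanish and English items, and the two groupings it names are incomplete substitutes. At Spanish shares of 25-50% of Latino fathers, the planned contrast is clearly less able to detect a moderate to large fault than a language contrast. At about 75% it usually flags the item without identifying the cause.

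The omission and the dilution formula are firm. The percentages are illustrative: the number of Latino fathers, their Spanish share, the shift size and the contrast of Latino fathers with all others are assumptions. That the survey is fielded in Spanish is inferred from eligibility, the Spanish advertisements and the cognitive-interview text, since the survey attachment was not available.

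The consequence is for SA 2 scale construction and for level-based Study 2 analyses. It does not undermine the Study 3 feasibility conclusions. This is a worthwhile, inexpensive improvement, not a fundamental defect.

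**What to change.** - Keep the survey language version as a variable for every Study 2 father.
- In G2, add it as a third DIF grouping: Spanish versus English responders within Latino fathers, reported beside the race/ethnicity DIF. A contrast against all English responders has more power but is confounded with ethnicity.
- Apply the G1 guide of 100 per group. If either language has fewer than 100 Latino fathers, label the result descriptive.
- Judge flagged items on effect size and item content together, not on a 0.5-logit cut alone, given the expected false flags.
- Leave confirmed items out of any score pooled over languages, or report scores by language. Treat a re-translated item as untested until it has been fielded again.

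The analysis costs one extra contrast on data already planned. The downsides are limited power for small shifts, a result that may only be descriptive because no language quota is set, and the expense of refielding if an item is re-translated.
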